3.1 Description of management strategies

The CONFORM protocol version 2.0 provides a more detailed description of the OH strategies. The CONFORM study is analysing the following management strategies.

- Conservative management In this study, non-pharmacologic therapy is standard first-line care and represents the control arm of the trial.
- Fludrocortisone with conservative management -The typical starting dose will be 100 micrograms, and the highest amount used in this study will be 400 micrograms. The PI has judged participants to be frailer and may have a lower starting dose of 50 micrograms.
- Midodrine with conservative management The recommended dose range is 2.5 milligrams three to 10 milligrams three times a day. Within this study, lower frequencies and doses may also be accepted.

The duration of follow-up for the three arms is 12 months from randomisation.

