NHS tariffs for conservative intervention will be used in sensitivity analysis, and the results compared to the micro-setting will be estimated using the methods described above.

Cost of Fludrocortisone

As described above, individuals will receive a starting dose of 10m micrograms daily; frailer patients may receive a starting dose of 50 micrograms. This decision will be based on the discretion of the clinician. Clinicians will be encouraged to titrate towards the highest clinically effective dose. As suggested by the British National Formulary (BNF), the highest dose used within this trial is 400 micrograms; however, most sites will use the maximum dose of 300 micrograms as this is the usual practice. The dummy tables used to estimate these costs are shown in the Appendix, Table 5.2.

The unit costs of the Fludrocortisone will be derived from the BNF ⁽¹⁷⁾. The BNF documents the costs per pack of Fludrocortisone and the number of tablets in a pack allowing for the cost per tablet to be calculated by dividing the number of tablets by the cost per pack. The number of tablets used per dose will be calculated by dividing the dose from the protocol by the mass of the tablet. The cost per tablet will be multiplied by the number of tablets used per dose to calculate the total daily costs. Total costs will be calculated by multiplying the total cost per day by the time horizon in days.

- cost per tablet = cost per pack/number of tablets in a pack
- number of tablets used per dose = dose from protocol/ mass of tablets
- total costs per day = cost per tablet X number of tablets used per dose
- total costs = total costs per day X by time horizon in days

In addition, the costs of the clinicians administering the therapy can be identified in the Unit costs of health and social care and NHS tariffs ^(15, 18). The staff costs for administering the medication will be getting the grade of the staff, which the research team will confirm. The hourly rate of this staff will be retrieved from the Unit cost of health and social care. The research team would estimate the mean time required to administer Fludrocortisone. Staff costs per session will be calculated by dividing the

hourly staff rate by the time needed to help with the medication. Total staff costs will be calculated by multiplying staff costs per session by the number of sessions.

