The estimates of the unit costs of Fludrocortisone will be added to the staff costs of administering. Total costs will be calculated for each participant, and an average cost per arm will be summarised as the average total resource use and total intervention cost per arm.

Cost of Midodrine

Participants who are randomised to Midodrine with conservative management will typically receive a starting dose of 2.5mmg TDS orally. Depending on the discretion of the clinician, lower doses and frequencies may be accepted. The maximum dose in this study is 10 mg. The costs of Midodrine will be estimated by the same method used for Fludrocortisone explained in the paragraph above, and the unit cost can be found in the BNF ⁽¹⁹⁾. The dummy tables used to estimate these costs are shown in the Appendix, Table 5.2.

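### The written daily drug-cost formula leaves out doses per day, so if used literally it would understate midodrine tablet cost (one third of the cost at three doses a day)

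*SAP*

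**What the plan says.** Section 3.3.2 of the SAP, under the cost of fludrocortisone, gives a chain of formulas after the cost per tablet. The tablets needed for one dose are found by dividing the protocol dose by the tablet strength. The daily cost then follows as "total costs per day = cost per tablet X number of tablets used per dose". The last step scales that daily figure up to the number of days in the time horizon.

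The prose above the bullets says the same thing. Fludrocortisone is described there as a daily dose ("micrograms daily; frailer patients may receive a starting dose of 50 micrograms"), and Appendix table 6.2.2 enters a frequency of 1 in every row.

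For midodrine, section 3.3.2 says that participants "will typically receive a starting dose of 2.5mmg TDS orally", and then: "The costs of Midodrine will be estimated by the same method used for Fludrocortisone explained in the paragraph above". It adds that lower doses and frequencies may be accepted, and it points to the Appendix dummy tables as the tool for the estimate. (The text calls these Table 5.2; in the Appendix they are numbered 6.2.) Table 6.2.4, the midodrine medication table, has a column for frequency per day, but its cells are empty.

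The top of the midodrine range is stated in two ways. Section 3.1 has "10 milligrams three times a day". Section 3.3.2 has "The maximum dose in this study is 10 mg", with no frequency attached, and the maximum-dose row of table 6.2.4 likewise gives the dose alone.

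**The concern.** The product of price per tablet and tablets per dose is the cost of a dose. Calling it the cost of a day is harmless for fludrocortisone at one dose a day. It is wrong for a drug taken several times a day, and the SAP explicitly carries it over to such a drug. This is a wrong rule, stated in both prose and formula; it is not merely a missing detail.

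The error would not cancel between arms. Fludrocortisone tablet cost would be right, conservative management alone has no trial-drug cost, and only midodrine would be too cheap. Its incremental drug cost would therefore be too low against both comparators. A cost or high-dose scenario built on the same formula would inherit the fault.

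**Working it through.** **Inputs.** Fludrocortisone, from table 6.2.2: £8.06 per pack, 30 tablets of 100 micrograms, frequency 1, 365 days. Midodrine, from sections 3.1 and 3.3.2: three times a day, with lower frequencies allowed. I take twice and once a day as the possible lower values; the SAP does not list them. It prints no midodrine price or tablet strength.

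**Step 1: reproduce the SAP's own figures.** Cost per tablet = 8.06 / 30 = £0.2687. Over 365 days by the written formula, using the unrounded price:

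- 100 micrograms: 0.2687 × 1 × 365 = £98.06
- 50 micrograms: 0.2687 × 0.5 × 365 = £49.03
- 300 micrograms: 0.2687 × 3 × 365 = £294.19

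All three match table 6.2.2. Multiplying by a frequency of 1 changes nothing, so these rows cannot show whether the table is meant to multiply by frequency.

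**Step 2: midodrine in general terms.** Let c be the cost per tablet, t the tablets per dose and f the doses per day.

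- Written formula: daily cost = c × t
- With frequency: daily cost = c × t × f
- Ratio of the first to the second = 1/f, whatever c and t are

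| Doses per day (f) | Share of tablet cost captured |
|---|---|
| 3 | 33.3% |
| 2 | 50% |
| 1 | 100% |

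**Step 3: in tablets.** Assume a 2.5 mg tablet. At 2.5 mg per dose, three times a day, over 365 days, the written formula counts 1 × 365 = 365 tablets; with frequency the count is 1 × 3 × 365 = 1,095. At 10 mg per dose, three times a day, the counts are 4 × 365 = 1,460 and 4 × 3 × 365 = 4,380. The ratio is one third in both cases.

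**Step 4: illustration in money.** Assume £0.30 to £1.00 per tablet and one tablet per dose; nothing in the SAP anchors either value.

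- Written formula: 0.30 × 365 = £109.50, up to 1.00 × 365 = £365 a year
- With f = 3: £328.50, up to £1,095 a year
- Shortfall: £219 to £730 a year
- At the £20,000 per QALY of section 3.5: 219 / 20,000 = 0.011, up to 730 / 20,000 = 0.037 QALY

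Only the ratio in step 2 rests on the document. The figures in step 4 show scale under assumed prices.

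**The case against.** The strongest reply is that the SAP already holds the missing input. The dummy tables are named as the costing tool, and both medication tables carry frequency per day as a column ahead of total cost per day. Its natural use is as a multiplier, so an analyst filling in table 6.2.4 might well apply it. Section 3.5.2 also speaks of varying the tablets used in a day. This stands in part: a reader might infer that midodrine is in fact costed at one third of its true cost, and the SAP does not support that. No midodrine cost has been computed, and one third applies only at three doses a day. It does not make the formula right. No stated calculation uses the column, the worked rows are silent because frequency is 1 throughout, and the text and the table disagree.

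A second reply is that the analyses most affected have gone. Section 2 describes section 3 as the originally planned analysis, and section 4.2 no longer proposes a complete within-trial evaluation; its four replacement analyses are descriptive. This stands. A reader might infer a biased base case and a biased dose sensitivity analysis, but those consequences largely fall away. What survives is the early economic model of section 4.2. That section does not say which drug-costing method the model will use, so bias there is a possibility and not a stated fact. Section 3.3.2 is, however, the only drug-costing method in the document.

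Third, the 10 mg maximum in section 3.3.2 comes shortly after the three-times-daily regimen and may be shorthand for a per-dose maximum. That is plausible, and it is a reason to ask for consistent wording, not to count it as a separate error.

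**Conclusion.** The point holds as a defect in the written rule. The formula omits the frequency term that the Appendix tables carry, and section 3.3.2 applies it unchanged to a drug typically started three times a day. Used literally, it gives 1/f of the midodrine tablet cost. It leaves fludrocortisone at one dose a day unchanged, so midodrine's incremental drug cost would be understated against both comparators. Staff and conservative-management costs are not touched by this formula.

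The factor needs no assumption about price or tablet strength, but it does depend on the frequency actually taken. The practical effect is conditional on the early economic model, or later work, using this formula as written. If the model did so, too low a midodrine cost would enter the comparison behind the value-of-sample-information calculation, which is meant to size a definitive trial. The money and QALY figures should carry no weight in judging seriousness. This should be fixed before the method is used again; it does not invalidate the descriptive analyses of section 4.2.

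**What to change.** In section 3.3.2, change both the prose and the bullet to: total cost per day = cost per tablet × tablets per dose × frequency per day, for both drugs. State that tables 6.2.2 and 6.2.4 calculate total cost per day in this way. Use the recorded frequency where it is available; where it is not, state the assumed frequency and vary it in sensitivity analysis. If the early economic model draws on section 3.3.2 for drug costs, say so and use the amended formula.

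Reconcile the statements of the midodrine maximum in section 3.1, section 3.3.2 and table 6.2.4, so that dose and frequency are given consistently. Which statement is correct is for the trial team to settle.

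The cost is a few words of text. The column already exists, and the three fludrocortisone figures in table 6.2.2 do not change.

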3.3.3 Costs of NHS Resources

During the following-up period, participants may utilise additional healthcare resources. Examples of Primary care resources can include GP, nurse/or other healthcare professional consultations. Primary care consultations can occur in various places, healthcare providers' various places, healthcare providers' various places, healthcare providers' practices, the participant's home, and over the telephone (including phone calls to NHS call centres). Secondary care resource use can refer to A and E departments, outpatient visits, and hospital admissions, which could be a day or overnight.

The Health Utilisation Questionnaires are used to capture the use of primary care services, including the number of contacts with GP, nurses, and " other health professionals" "". We aim to capture all potential forms of primary care costs were captured. For example, primary care consultations may be face-to-face at the practice, at the " 'participant's home, or by telephone. The differentiation is important as the cost of each of these varies (see below on derivation of unit costs). Secondary

care refers to visits to an A & E department, outpatient clinics and hospital admissions as a day patient or as an inpatient (inpatient admissions are defined as where the person stays at least one night in the hospital).

Healthcare resource use is associated with different unit costs, regardless of whether these resources are primary or secondary. Details of resource use of primary and secondary care will be captured using the e-CRF and follow-up Health Utilisation Questionnaires at baseline, three months, six months, and 12 months after the trial. The dummy tables used to estimate these costs are shown in the Appendix, Table 5.3.

The number of face-to-face or phone appointments with their GP or nurse within a specific time horizon will be extracted from the e-CRF. The cost per minute and the mean length of consultation in minutes can be removed from the Unit cost of health and Social Care ⁽¹⁵⁾. The costs per consultation will be multiplied by the number of appointments within a time horizon to calculate the total staff costs per patient for each patient, thus allowing us to calculate the average staff per patient for each intervention arm. The dummy tables used to estimate these costs are shown in the Appendix, Table 5.3.

The ambulance service unit cost can be extracted from the NHS cost Schedule. The NHS cost Schedule lists four different types of ambulance services ⁽¹⁸⁾. The average unit costs will be calculated, and the average costs will be multiplied by the number of visits within a particular time horizon to calculate the total cost of ambulance services per patient. The average cost per patient would then be calculated for each other three intervention arms. The dummy tables used to estimate these costs are shown in the Appendix, Table 5.3.

An average of the unit costs of the Accident & Emergency currency descriptions with the highest number of data submissions (any currency description with a number of data submissions higher than 110 will be included in the average)⁽¹⁸⁾. Accident and emergency services unit costs will be extracted from the NHS cost Schedule. The total cost will be calculated by multiplying the unit cost by the number of appointments documented in the e-CRF. The average Accident and emergency services cost will then be calculated for each of the three intervention arms. The dummy tables used to estimate these costs are shown in the Appendix, Table 5.3.

3.3.4 Cost of Private Services (non-NHS) Care

The cost of private services and the number of particular visits will be extracted from the e-CRF. Private services include things such as physiotherapy and acupuncture. First, the total cost for each private patient service will be calculated by multiplying the number of private service visits by the amount each patient paid for the private service they used. Then, the private costs will be grouped with the same theme. Finally, the average costs of private services for each of the three arms will be calculated. The dummy tables used to estimate these costs are shown in the Appendix, Table 5.3.

3.3.5 Cost of Personal Social Services

The e-CRF will allow us to determine what social benefit each participant receives. These benefits include Attendance Allowance, Pension Savings Credit, and Pensions Guarantee Credit; the cost of these benefits can be found on the the.Gov.UK website ^(20, 21). These costs will be multiplied by the length of the time horizon to calculate the total cost per participant. We will then be able to calculate the average cost of benefits per intervention. A sensitivity analysis would be used to see how the cost-effectiveness would vary if we used the lowest rate compared to the highest. The dummy tables used to estimate these costs are shown in the Appendix, Table 5.3.

The number of social service consultations a participant uses within a given time horizon can be derived from the e-CRF. The Unit Cost of Health and Social Care reports the cost of social care per hour ⁽¹⁵⁾. The research team would confirm the mean time one can expect for a social service consultation. Collecting data on the mean length of time will allow us to calculate the average cost of social service intervention. The average cost of social care can be multiplied by the number of social care appointments to calculate the total cost of social care. The total social costs would allow us to calculate the average cost of social per treatment arm.

3.3.6 Time and Travel Questionnaire

The time and travel questionnaire will assist in gathering information on the cost of accessing healthcare resources relating to Orthostatic Hypotension. The questionnaire captures information about the amount of time and money the participant and a 'participant's family member or carer have spent using health care services six months after. The time and travel questionnaire are split into three sections with 12 questions.

The three sections are:

- Hospital outpatient appointments
- Hospital admissions
- GP / Nurse/Walk-in Centre visits

For each of the three sections on the questionnaire, the cost of travel and the opportunity cost in monetary terms for each study participant and the people accompanying them to the appointments will be summated, and an average will be calculated for each treatment arm. In addition, the average cost and opportunity cost will be calculated per participant and the person accompanying the appointment. The dummy tables used to estimate these costs are shown in the Appendix, Table 5.4.

Hospital Outpatients Appointments

This set of questions referred to hospital appointments. Participants who did not have a hospital appointment were told to proceed to the next section. The questionnaire captured information about the mode of transport a participant used to go to a hospital appointment to their most recent. The cost of travel to this appointment for those who used public travel will be extracted from the questionnaire; the time spent travelling to this appointment and the length of time spent at this appointment will also be collected.

The travel costs of those who arrived and used ambulance services to attend the appointment will be derived from the average unit cost of ambulance services from the NHS reference list ⁽¹⁸⁾. The distance travelled to the appointment was also

recorded for the participants that travelled by car, walked or cycled. The cost per mile will be extracted from the advisory fuel rates.Gov.uk website ⁽²²⁾. The price per mile will be multiplied by the distance travelled to the appointment to calculate the total cost travelled by car. For those that walked and cycled, the cost of travel was not recorded. Instead, the average trip price, the average time spent travelling to an appointment, and the average time spent during an appointment per participant will be calculated for all modes of transport.

Estimates of the opportunity costs of the appointment will be calculated from the questionnaire. Participants will be asked about their main activity if they were not attending the appointment. The national median hourly wage will be calculated using the Office of National Statistics data for the participants who would have been in paid work. This hourly rate will be multiplied by the time spent travelling to and attending the appointment to calculate the opportunity cost of paid work for each employed participant. The opportunity costs of being a homemaker will be calculated by multiplying the national minimum wage, which can be found on the Gov. UK website, by the time, spent travelling to and attending the appointment (²³).

A similar process will be used to calculate the opportunity cost for that hourly rate for childcare will be collected from the Coram Childcare Survey 2022; this will be multiplied by the time spent travelling to and attending the appointment ⁽²⁴⁾. The opportunity costs for caring for friends and family would be calculated using the same method mentioned above using the hourly rate of care derived from the UK Care Guide ⁽²⁵⁾. The opportunity costs of those who are retired will be calculated similarly using the state pensions, which can be found on the UK government website ⁽²⁶⁾. The student finance website will be used to provide data needed to calculate the opportunity cost of full-time education. ⁽²⁷⁾.

Similar methods will be used to calculate the opportunity costs of unemployed people by deriving the average monthly allowance from universal credit ⁽²⁸⁾. The standard monthly budget for universal income varies depending on age and marital status. For this trial, we will assume participants are single and older than 25. The opportunity costs for volunteering would be calculated using information from the Office for National Statistics ⁽²⁹⁾. The Office for National Statistics will provide data on

average expenditure on recreation and culture, which will be used to calculate the opportunity costs of leisure activities.

A similar process was conducted to calculate the opportunity costs of the family member, friend or carer accompanying the study.

3.3.6 Adverse Events

Information on adverse events, AEs, and serious adverse events (SAE) will be collected via the electronic e-CRF at any time during the trial. AEs may require additional medications or hospitalisation. The cost of the AE will be estimated by calculating the cost of the action taken to resolve the AE. The three possible actions that could be taken are reducing the dose and withdrawing the Investigational Medical Product. IMP or no action. The intervention cost will be calculated as described above until the resolution is conducted for participants who had a dose reduction or no longer received their IMP; as a result, AE Reducing the dose would alter the inputs needed to calculate the intervention costs from the resolution date. The resolution date allows us to calculate the cost of AE over a specific period. A withdrawal of the IMP at a given resolution date will result in only the costconservative management calculated from the resolution date. For participants that did not require any action due to the AE, the intervention cost was calculated similarly to the overhead cost of the intervention section. The total cost of adverse events for each intervention will be calculated, thus allowing us to calculate the average prices.

3.3.7 Estimation of total costs

The mean total cost of each intervention group will be calculated by summing the costs of interventions, NHS resources, Private Services, Personal Social Services, Time and Travel and Adverse Events for each participant and then dividing by the number of participants included in the analysis are added together. A sensitivity analysis will be conducted for each cost input to assess the effect of high and low estimates of costs.

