The key objective of this economic plan is to outline how an economic evaluation will be carried out as part of the CONFORM-OH trial. It was planned that the study will include a within-trial cost-utility analysis with a longer-term model-based extrapolation to estimate the incremental cost per quality-adjusted life-years (QALYs). QALYs will be derived based on responses to the EQ-5D-5L. The rationale behind using a model-based analysis and a trial-based analysis is that the results of the within-trial study might indicate that a treatment strategy for Orthostatic Hypotension is not cost-effective. Still, it is plausible that extrapolation might change this conclusion. However, the converse can also occur, where a strategy initially found to be cost-effective becomes cost-ineffective when longer-term costs and effects are considered. Therefore, an economic evaluation model was planned to extrapolate cost and QALYs beyond the 12-month trial follow-up period. Section 4 presents further details of this analysis.

The perspective of the CONFORM trial is that of the UK National Health Service (NHS) and Personal and Social Services (PSS). Healthcare resource use will be the main cost of this economic evaluation. The economic assessment will calculate the average cost to the NHS of interventions, conservative management plus Fludrocortisone and conservative management plus Midodrine. We will also calculate the average costs of the comparator, conservative management. A sensitivity analysis will explore a broader perspective considering the price falling on individuals or their families/carers. Within the sensitivity analysis, this cost will include direct, e.g., out-of-pocket costs of any medications or therapies purchased and indirect costs such as time off, paid work and travel, and costs to the NHS.

The within-trial economic evaluation was planned to report the following economic outcomes:

- NHS cost of managing individuals with Orthostatic Hypotension over 12 months.
- Direct and indirect costs fall on individuals who suffer from Orthostatic Hypotension and their families/carers over 12 months.

- QALYs estimated based on responses to the EQ-5D-5L administered at baseline, three, six, and 12 months post-randomisation.
- The incremental cost-effectiveness ratio (ICER) is the incremental cost per QALY gained for a more effective but more costly intervention than a less costly but less effective one.

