3.5.2 Sensitivity analysis

A stochastic/probabilistic and deterministic sensitivity analysis will be conducted to characterise the uncertainty.

Stochastic sensitivity analysis

A stochastic sensitivity analysis will be conducted. Bootstrapping techniques will be utilised in this analysis ⁽³⁵⁾. (Bootstrapping can be described as the non-parametric technique used to estimate the distributions of important statistics relevant to the model, such as the ICER.⁽³⁶⁾. Stochastic analysis would explore the potential effects of statistical imprecision of parameters used within the model on costs effects and cost-effectiveness estimates if the sampling process could be repeated many times. Random values will be selected from the cost and QALY data retrieved from the trial. When a random value is used for the bootstrap resample, it is returned to the original sample. Consequently. A bootstrapped dataset derived from the complete case data on costs and outcomes from each trial arm.

This process will be carried out many times (e.g., 1000, 5000, 10,000), creating a sample of bootstrapped mean costs and QALYs with their corresponding distributions. The bootstrapped distribution will be calculated using bootstrapped costs, QALYS, and other parametric statistics. The results from the bootstrapping will be presented as a cost-effectiveness plane to demonstrate the distribution of incremental costs and incremental effects, allowing us to identify the distribution of total incremental costs and incremental effects. The horizontal axis will represent the QALYs difference between the two interventions, and the vertical axis will represent the corresponding cost difference. The bootstrapped results will also be presented

as cost-effectiveness acceptability curves (CEACs). CEACs enable us to identify the management strategy that maximises net benefits at each willingness to pay value for additional QALYs gained) ⁽³⁷⁾.

Deterministic sensitivity analysis

Deterministic sensitivity analysis will be used to assess the effect of assumptions such as dose of medications, method of conservative management and unit costs on the results using best-case and worst-case scenario analysis. A societal perspective will be used to explore the impact of patient costs on cost-effectiveness results. The results from the deterministic analysis will determine how the analysis will be performed, including one-way, two-way or multiway analysis.

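### The only total-cost rule mixes patient-borne costs and cash benefits into a total that the plan says is NHS and PSS

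*SAP*

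**What the plan says.** **Perspective.** SAP section 2 states: "The perspective of the CONFORM trial is that of the UK National Health Service (NHS) and Personal and Social Services (PSS". The same paragraph continues: "A sensitivity analysis will explore a broader perspective considering the price falling on individuals or their families/carers". It describes that broader view as covering "out-of-pocket costs of any medications or therapies purchased and indirect costs such as time off, paid work and travel, and costs to the NHS". Section 3.5.2, under deterministic sensitivity analysis, repeats the arrangement: "A societal perspective will be used to explore the impact of patient costs on cost-effectiveness results".

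**Total cost.** Section 3.3.7 forms the mean total for each arm by "summing the costs of interventions, NHS resources, Private Services, Personal Social Services, Time and Travel and Adverse Events for each participant" and dividing by the number of participants analysed. Section 3.5 takes total cost and QALYs by arm into the ICER. No other total is defined.

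**What the components contain.**
- Private services (3.3.4) are costed by "multiplying the number of private service visits by the amount each patient paid for the private service they used".
- Time and travel (3.3.6, Time and Travel Questionnaire) covers travel and opportunity costs of participants and of those accompanying them. Unemployed people's time is priced by "deriving the average monthly allowance from universal credit".
- Personal Social Services (3.3.5) covers social service consultations and also cash benefits: "These benefits include Attendance Allowance, Pension Savings Credit, and Pensions Guarantee Credit". Table 6.3.4 adds, among others, Personal Independence Payment, Employment and Support Allowance, Universal Credit and Carer's Allowance.

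**After early closure.** Section 2 says that section 3 records the within-trial analysis as it was planned and that section 4 gives the plan for the data now available. Section 4.2 replaces the full evaluation with completion rates, summaries by resource area, EQ-5D-5L summaries, and an early economic model with a value-of-information calculation.

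**The concern.** A cost total has to match the declared perspective. Followed literally, 3.3.7 yields a figure that is neither NHS and PSS cost nor a clearly labelled societal cost. Items that sections 2 and 3.5.2 reserve for a sensitivity analysis are already in the main total, so the contrast between the two perspectives is blurred.

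The cash benefits raise a separate problem. They are transfers of money, not health or social care resources used. They also depend on entitlement, so a chance imbalance between arms in who receives them would appear as a cost difference. Using the Universal Credit rate both as a benefit cost and as the price of unemployed participants' time risks double counting in a total that holds both.

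At stake now are three things: whether benefits are reported under a social-care heading and passed on in that form to later evidence synthesis; what any presented total means; and which costs enter the early model. Section 4.2 states no cost perspective for that model, yet the choice affects net benefit, decision uncertainty and so the sample size that the value-of-information work is meant to inform.

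**Working it through.** The point rests on comparing sections. No figure in the plan is in dispute.

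**1. Components of 3.3.7 against the declared perspective**

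| Component | Costed in | Fits NHS and PSS? |
|---|---|---|
| Interventions | 3.3.2 | Yes |
| NHS resources | 3.3.3 | Yes |
| Adverse events | 3.3.6 (Adverse Events) | Yes, if not already counted elsewhere |
| Social service consultations | 3.3.5, Table 6.3.5 | Yes |
| Cash benefits | 3.3.5, Table 6.3.4 | No: transfer payments |
| Private services | 3.3.4 | No: paid by the patient |
| Time and travel | 3.3.6 (Time and Travel) | No: mainly borne by participant and companion |

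The benefits are not collected for description alone. Section 3.3.5 multiplies them by the time horizon and plans a sensitivity analysis of cost-effectiveness between the lowest and highest rates.

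**2. The plan's own drug costs, for scale**

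Inputs from Table 6.2.2: £8.06 a pack, 30 tablets, 365 days. Annual cost = 8.06 / 30 × tablets per day × 365.
- 0.5 tablet: £49.03, or £0.94 a week
- 1 tablet: £98.06, or £1.88 a week
- 3 tablets: £294.19, or £5.64 a week

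All three annual figures reproduce the table. A mean between-arm difference in out-of-perspective items equal to one of these weekly amounts would match the corresponding whole annual drug cost.

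**3. Cash benefits (assumed rates; the SAP gives none)**

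Assume £60 to £100 a week per recipient.
- Per recipient-year: 60 × 52 = £3,120; 100 × 52 = £5,200
- Relative to £98.06: 31.8 to 53.0 times. Relative to £294.19: 10.6 to 17.7 times
- Each percentage point of imbalance in receipt: £31.20 to £52.00 per participant
- An assumed 5-point imbalance: £156 to £260, equivalent at the plan's £20,000 per QALY to 156 / 20,000 = 0.008 up to 260 / 20,000 = 0.013 QALY

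**4. Time and travel (assumed)**

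Two people × 2 hours × £10 to £15 an hour = £40 to £60 for one accompanied appointment.

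**5. Effect on a cost per QALY (assumed QALY difference)**

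Shift = cost difference / QALY difference. For £100 of out-of-perspective cost: 100 / 0.01 = £10,000 per QALY; 100 / 0.05 = £2,000 per QALY. This would bear on a cost-per-QALY result from the early model if its inputs followed 3.3.7. It does not describe a trial ICER, since none is now planned.

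**The case against.** The strongest reply is that section 3 is largely superseded. The summaries in section 4.2 need no total at all, so nothing that moves a trial ICER across £20,000 can follow. This stands, and it is the main reason to rate the point lower.

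It can also be said that 3.3.7 never calls its sum the base case, and that section 2 lists NHS costs and costs to individuals as separate outcomes. On that view 3.3.7 merely lists components without splitting them. That may well be the intention, but no NHS/PSS-only total is written anywhere. Section 4.1 adds to the uncertainty by naming participant and family costs among the within-trial costs.

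A reader might infer several stronger things that the document does not support:
- *That the broader sensitivity analysis would add nothing.* Section 2 includes purchased medicines and time off work. Sections 3.3.4 and 3.3.6 cost private service visits and appointment-related time, so part of the broader view lies outside the 3.3.7 sum.
- *That Universal Credit is definitely counted twice.* One use records receipt and the other prices time. They share a rate, which makes double counting a risk, not a certainty.
- *That benefits would dominate the result.* Drug cost is a small comparator. Admissions, emergency care and staff time are also in the total, and no receipt rate or arm size supports the 5-point imbalance.
- *That the 3.3.7 list automatically feeds the early model.* Section 4.2 draws on trial data, literature and expert opinion without citing 3.3.7. Section 4.1 describes the earlier model in NHS and PSS costs, while section 2 also lists individual and family costs among its outcomes. The early model's cost scope is therefore unsettled, not shown to be wrong.

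**Conclusion.** The inconsistency is established from the text: 3.3.7 conflicts with sections 2 and 3.5.2 on private services and on time and travel, and 3.3.5 with Table 6.3.4 classifies transfer payments as social services. The practical effect is confined to how resource areas are classified and reported, any totals that are presented, and the costs entering the early model and its value-of-information result.

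Its numerical size cannot be derived from the SAP. The benefit rates, receipt imbalance, hourly values and QALY differences used above are assumptions. They show only that modest differences in out-of-perspective items can be as large as the tabulated drug costs. The point should be corrected before totals are reported or the model is built, but it is not a critical defect given the close-down plan.

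**What to change.** In section 3.3.7 define two totals:
1. **NHS/PSS total** = interventions + NHS resources + social-care contacts + adverse-event costs not already counted in interventions or NHS resources. The qualifier is needed because the adverse-event section builds its cost partly from intervention cost after a dose change or withdrawal.
2. **Broader-perspective total** = total 1 + private services + time and travel, for the sensitivity analysis named in sections 2 and 3.5.2.

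Take cash benefits out of the Personal Social Services heading in 3.3.5 and Table 6.3.4, and report them separately as transfers outside both totals. This also removes the Universal Credit overlap. State in section 4.2 that the early economic model uses total 1 as its base case.

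The cost is wording and one extra derived variable; no new data are needed. The small downside is that benefits no longer appear in any total.
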